13.7 Safety Analysis

Safety and tolerability will be assessed by AEs, laboratory testing (haematology, biochemistry, and urinalysis), and vital signs.

The safety analyses will be performed using the safety population (Section 13.2). Treatment-emergent AEs will be classified using the Medical Dictionary for Regulatory Activities (MedDRA) classification system. All AEs will be summarized by system organ class, preferred term, severity, and relationship to IP. Adverse events leading to death or to discontinuation from treatment and SAEs will also be tabulated. In the by-subject analysis, a subject having the same event more than once will be counted only once and by greatest severity.

Laboratory data will be summarized descriptively by visit. In addition, shift tables showing the number of subjects with values low, normal, and high compared to the normal ranges pretreatment versus post-treatment will be provided.

Vital sign measurements, including weight, will be summarized descriptively by visit and presented as shift tables.

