7.2.2 Secondary Safety Endpoints

The following safety parameters will be evaluated for the duration of the study:

- Type, frequency, severity, and relationship of AEs to investigational product (IP)
- Number of subjects who discontinue IP due to any AE
- Frequency of clinically significant changes in vital signs and/or laboratory findings

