10.2 Inclusion Criteria

Subjects must satisfy the following criteria to be enrolled in the study:

- 1. Male or female aged 18 and over at the time of signing the informed consent.
- 2. Must understand and voluntarily sign an ICF prior to any study-related assessments/procedures being conducted.
- 3. Must be able to adhere to the study visit schedule and other protocol requirements.
- 4. Diagnosis of UC with a duration of at least 3 months prior to the Screening Visit.
- 5. MMS ≥ 4 to ≤ 8 (range: 0 9) prior to randomization in the study
 - SFS > 1 and RBS = 1 or 2
 - Mayo endoscopic sub-score > 1 and < 3 prior to randomization in the study
- 6. Subjects are required to have a colonoscopy if one has not been performed within 12 months prior to the Screening Visit.
- 7. Subjects who have relapsed on maintenance therapy with doses of 5-ASA \leq 2.4 g/day.
- 8. Must meet the following laboratory criteria:
 - WBC count $\ge 3000/\text{mm}^3$ ($\ge 3.0 \times 10^9/\text{L}$) and $< 14,000/\text{mm}^3$ ($< 14 \times 10^9/\text{L}$)
 - Platelet count $\ge 100,000/\text{mm}^3 \ (\ge 100 \times 10^9/\text{L})$
 - Serum creatinine $\leq 1.5 \text{ mg/dL}$ ($\leq 132.6 \mu \text{mol/L}$)
 - AST (SGOT) and ALT (SGPT) ≤ 2 upper limit of normal (ULN). If initial test shows ALT or AST > 2 ULN, 1 repeat test is allowed during the screening period
 - Total bilirubin ≤ 2 mg/dL (≤ 34 mol/L) and albumin > lower limit of normal (LLN). If initial albumin test result is < 2 g/dL, 1 repeat test is allowed during the screening period
 - Hemoglobin $\geq 9 \text{ g/dL}$ ($\geq 5.6 \text{ mmol/L}$)
- 9. FCBP must have a negative pregnancy test at screening and the Baseline Visit. While on IP and for at least 28 days after taking the last dose of IP, FCBP who engage in activity in which conception is possible must use one of the approved contraceptive options² described below:

Option 1: Any one of the following highly effective methods: hormonal contraception (oral, injection, implant, transdermal patch, vaginal ring); intrauterine device (IUD); tubal ligation; or partner's vasectomy

OR

- **Option 2:** Male or female condom (latex condom or nonlatex condom NOT made out of natural [animal] membrane [for example, polyurethane]); PLUS one additional barrier method: (a) diaphragm with spermicide; (b) cervical cap with spermicide; or (c) contraceptive sponge with spermicide

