15 DISCONTINUATIONS

The following events are considered sufficient reasons for discontinuing a subject from the IP and/or from the study:

- Lack of therapeutic effect after at least 4 weeks
- Withdrawal of consent
- Death
- Lost to follow up
- Protocol violation
- Study terminated by sponsor
- Pregnancy
- Unexplained weight loss $\geq 7.5\%$ from baseline

The decision to discontinue a subject remains the responsibility of the treating physician, which will not be delayed or refused by the sponsor. However, prior to discontinuing a subject, the Investigator may contact the Medical Monitor and forward appropriate supporting documents for review and discussion. The reason for discontinuation should be recorded in the eCRF and in the source documents.

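### Section 13.7 plans no count of the clinically significant changes that Section 7.2.2 makes an endpoint, and its low/normal/high laboratory shift tables cannot show how large a worsening is

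*Combined protocol and SAP*

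**What the plan says.** Section 7.2.2 lists as a secondary safety endpoint "Frequency of clinically significant changes in vital signs and/or laboratory findings". It stands beside, and separate from, the endpoints on adverse events (AEs) and on discontinuation due to AEs. No section says what size of laboratory or vital-sign change is clinically significant.

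Section 13.7 gives the analysis. For laboratory tests: "Laboratory data will be summarized descriptively by visit". A second laboratory output consists of "shift tables showing the number of subjects with values low, normal, and high compared to the normal ranges", set out by level before and after treatment. For vital signs: "Vital sign measurements, including weight, will be summarized descriptively by visit and presented as shift tables". The three named levels belong to the laboratory sentence; the vital-sign sentence names none.

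Section 10.2, criterion 8, sets the entry limit "AST (SGOT) and ALT (SGPT) ≤ 2 upper limit of normal (ULN", so values above normal and up to twice the upper limit are admitted. The hemoglobin floor is 9 g/dL. Albumin, by contrast, must lie above the lower limit of normal.

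Section 15 lists "Unexplained weight loss" of at least 7.5% from baseline among the reasons for discontinuation. Section 13.1 describes Section 13 as an outline and leaves the full plan to a separate SAP.

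**The concern.** An endpoint stated as a frequency needs a rule for what counts and a table that counts it. The text gives neither. The nearest planned output is a three-level shift table, which records only whether a value crossed a normal limit. It gives a small crossing the same weight as a large one, and it shows nothing when a subject who starts out of range gets worse in the same direction.

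The size of change matters in this trial. According to Section 5.5, 320 mg/day has been given only as single doses in healthy volunteers, the 8-week experience is at 160 mg/day, and the formulation is new. The one related event graded severe so far was itself a laboratory finding, a transient rise in amylase shown to be salivary. If laboratory tolerability of the two doses is to be compared with placebo, the planned categorical table discards much of the relevant information.

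**Working it through.** No stated figure in the plan bears on this point, so the check is whether the planned tables can show the changes the endpoint describes.

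**Inputs.** AST/ALT entry limit of 2 x ULN and hemoglobin entry floor of 9 g/dL (Section 10.2); three shift levels (Section 13.7); 69 subjects per arm (Section 8.1). Assumption: a hemoglobin lower limit of normal between 11.5 and 13.5 g/dL, since the documents give none.

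**Rule.** A value is low if below the lower limit, high if above the upper limit, and otherwise normal. A shift is a difference between the pretreatment and post-treatment levels.

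**AST/ALT, in multiples of ULN:**

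| Pretreatment | Post-treatment | Ratio | Cell |
|---|---|---|---|
| 1.5 | 1.2 | 0.8 | high to high |
| 1.5 | 3 | 2.0 | high to high |
| 1.5 | 10 | 6.7 | high to high |
| 2.0 | 1.2 | 0.6 | high to high |
| 2.0 | 10 | 5.0 | high to high |
| 0.8 | 1.2 | 1.5 | normal to high |
| 0.8 | 10 | 12.5 | normal to high |

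For a subject who enters high, one cell holds both improvement and a several-fold rise. For a subject who enters normal, the table registers a rise but not its size. This needs no outside figure.

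**Hemoglobin.** Falls from 9.0 to 7.0 and from 10.5 to 8.0 g/dL are low-to-low at every assumed lower limit from 11.5 to 13.5. A fall of 0.2 g/dL across the limit (12.1 to 11.9 with a limit of 12) is a shift.

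**Do the by-visit summaries fill the gap?** If k of 69 subjects go from 1.5 to 10 x ULN and the rest are unchanged, the arm mean moves by k x (10 - 1.5)/69:

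- k = 1: 8.5/69 = 0.12 x ULN
- k = 2: 17/69 = 0.25 x ULN
- k = 3: 25.5/69 = 0.37 x ULN

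The median does not move if those subjects were already above it. A maximum, if reported, would show one extreme value, but neither how many subjects worsened nor from what baseline.

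**Weight.** A 7.5% loss at an illustrative 80 kg is 0.075 x 80 = 6.0 kg. One such subject moves the mean of 69 by 6.0/69 = 0.09 kg. Whether the shift table would show the loss cannot be determined, because its categories are not given.

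**What one extra cut does.** Split high at the entry limit, into above 1 to 2 x ULN and above 2 x ULN. Every rise in the table from 1.5 or 2.0 to 3 or 10 x ULN then becomes a shift, while 1.2 x ULN does not. Separating 3 from 10 x ULN needs further cuts.

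**The case against.** The strongest reply is that clinically important changes are captured elsewhere. Section 14.3 makes a laboratory abnormality an AE if it leads to discontinuation, needs treatment or a change to study drug, or is judged clinically important. Section 14.1 treats clinically significant worsening of a pre-existing condition as an AE. Section 13.7 tabulates AEs by preferred term, severity and relationship, and Section 13.5.1 summarizes the primary reason for discontinuation. A rise in ALT to 10 x ULN would be expected to enter those tables.

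This stands in part. A reader might infer that the endpoint is not measured at all; the documents do not support that, because the values are collected, summarized by visit and open to AE reporting. But the AE route sets no numeric limit, and Section 14.3 records only the diagnosis where an abnormality is part of one. Section 9.6.8 keeps non-serious UC worsening out of the AE record, so a hemoglobin fall or weight loss attributed to a flare may leave no AE. Section 7.2.2 also lists the laboratory endpoint separately from AEs.

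Three further inferences do not hold:

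- That the weight table cannot show a 7.5% loss. Low, normal and high are stated only for laboratory values, and percent-change categories would show it. Estimates based on BMI bands would describe a table nobody planned, as Section 9.6.3 calculates BMI at screening only. The 7.5% figure is a discontinuation reason for unexplained loss, not part of the endpoint definition, and subjects stopped for it appear in disposition. What is missing is a count that includes those who continue or are coded to another reason.
- That the Part 1 safety review shares the defect. Its scope is set in its own charter (Section 13.10).
- That every analyte is affected. Low albumin is not admitted, exclusion 17 removes abnormalities posing unacceptable risk, and worsening across the opposite limit would still show.

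Finally, a separate SAP may supply the missing detail. It is the natural place for it, but nothing in the available text commits it to do so.

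**Conclusion.** The point holds in limited form. The Section 7.2.2 endpoint has no objective definition and no planned tabulation in the available text. The three-level laboratory table cannot show further same-direction worsening in subjects who enter out of range, and the AST/ALT limit admits such subjects by its own terms. It also does not separate small from large rises in subjects who enter normal. The vital-sign and weight shift categories are unstated, which is an omission and not a demonstrated failure.

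The size is structural: up to a 6.7-fold rise from 1.5 x ULN shares a cell with an improvement, and the by-visit mean moves by 0.12 x ULN for one such subject in 69. The number of subjects affected cannot be derived, because the documents do not say how many will enter out of range. The AST/ALT result rests on the protocol's figures alone; the hemoglobin illustration rests on the assumed lower limits. No sample size, power or type I error figure is touched.

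**What to change.** In Section 13.7 or the separate SAP, before unblinding:

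1. Use graded shift bands for laboratory values. For AST and ALT, express them in multiples of ULN, with a cut at the protocol's own 2 x ULN entry limit and further cuts above it.
2. Define a clinically significant change from the subject's own baseline for each analyte and vital sign, and tabulate by arm the number and percentage of subjects who meet it. State the shift categories for vital signs.
3. Report weight as percent change from baseline, with the count of subjects reaching the 7.5% loss named in Section 15. This is a tabulation only and leaves the discontinuation rule unchanged.

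The cost is a few more tables from data already scheduled, and the work of agreeing limits for each analyte before the blind is broken. No visit, procedure or sample size changes.

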13.8 Pharmacokinetic Assessments

Nonlinear mixed effect models will be used for the evaluation of the population PK profile. The population PK analysis will be performed using NONMEM® software. The evaluation will be performed for describing the PK in the subject population and for identifying the relevant demographic and pathophysiological covariates.

The approach will be based on the development of the following 3 models:

- Identification of the structural model that best describe the pharmacokinetic data in absence of covariates.
- Random Effect Models: defining the inter-individual variability and the residual error. Different forms of residual error (additive, multiplicative or both) will be explored.
- Covariate Model: identifying the relevant demographic and pathophysiological covariates affecting the PK profile of the compound. The selection of the covariates will be performed using an appropriate statistical methodology.

13.9 Pharmacodynamic Assessments

The relationship between CRP and UC-DAI score will be assessed using scatter plots and correlations.

13.10 Interim Analysis

An interim safety review will be performed by an independent safety committee on data from the 24 subjects randomized into Part 1 of the study. The scope of this analysis will be documented prior to analysis in a safety committee charter. Initiation of Part 3 of the study will follow completion of this review.

14 ADVERSE EVENTS

14.1 Monitoring, Recording and Reporting of Adverse Events

An AE is any noxious, unintended, or untoward medical occurrence that may appear or worsen in a subject during the course of a study. It may be a new intercurrent illness, a worsening concomitant illness, an injury, or any concomitant impairment of the subject's health, including laboratory test values (as specified by the criteria in Section 14.3), regardless of etiology. Any worsening (ie, any clinically significant adverse change in the frequency or intensity of a preexisting condition) should be considered an AE. A diagnosis or syndrome should be recorded on the AE page of the eCRF rather than the individual signs or symptoms of the diagnosis or syndrome.

Abuse, withdrawal, sensitivity, or toxicity to an investigational product should be reported as an AE. Overdose, accidental or intentional, whether or not it is associated with an AE, should be reported on the drug exposure eCRF page. Any sequela of an accidental or intentional overdose of an investigational product should be reported as an AE on the AE eCRF. If the sequela of an overdose is an SAE, then the sequela must be reported on an SAE report form and on the AE eCRF. The overdose resulting in the SAE should be identified as the cause of the event on the SAE report form and eCRF but should not be reported as an SAE itself.

All subjects will be monitored for AEs during the study. Assessments may include monitoring of any or all of the following parameters: the subject's clinical symptoms; weight loss; diarrhea; laboratory; pathological; radiological or surgical findings; physical examination findings; or findings from other tests and/or procedures.

All AEs will be recorded by the Investigator from the time the subject signs informed consent until 28 days after the last dose of IP, and those SAEs made known to the Investigator at any time thereafter that are suspected of being related to IP. Adverse events and SAEs will be recorded on the AE page of the CRF and in the subject's source documents. All SAEs must be reported to PPM SERVICES SA Drug Safety within 24 hours of the Investigator's knowledge of the event by facsimile, or other appropriate method, using the SAE Report Form, or approved equivalent form.

14.2 Evaluation of Adverse Events

A qualified Investigator will evaluate all AEs as to:

14.2.1 Seriousness

An SAE is any AE occurring at any dose that:

- Results in death;
- Is life-threatening (ie, in the opinion of the Investigator, the subject is at immediate risk of death from the AE);
- Requires inpatient hospitalization or prolongation of existing hospitalization (hospitalization is defined as an inpatient admission, regardless of length of stay);

- Results in persistent or significant incapacity/disability (a substantial disruption of the subject's ability to conduct normal life functions);
- Is a congenital anomaly/birth defect; and/or
- Constitutes an important medical event.

Important medical events are defined as those occurrences that may not be immediately life threatening or result in death, hospitalization, or disability but may jeopardize the subject or require medical or surgical intervention to prevent one of the other outcomes listed above.

Medical and scientific judgment should be exercised in deciding whether such an AE should be considered serious.

Events **not considered** to be SAEs are hospitalizations for:

- A procedure for protocol/disease-related investigations (eg, scans, endoscopy, sampling for laboratory tests). However, hospitalization or prolonged hospitalization for a complication of such procedures remains a reportable SAE.
- Hospitalization or prolongation of hospitalization for technical, practical, or social reasons, in absence of an AE.
- A procedure that is planned (ie, planned prior to starting of treatment on study) must be documented in the source document and the CRF. Hospitalization or prolonged hospitalization for a complication remains a reportable SAE.
- Emergency outpatient treatment or observation that does not result in admission, unless fulfilling other seriousness criteria above.

If an AE is considered serious, both the AE page/screen of the CRF and the SAE Report Form must be completed.

For each SAE, the Investigator will provide information on severity, start and stop dates, relationship to IP, action taken regarding IP, and outcome.

14.2.2 Severity/Intensity

For both AEs and SAEs, the Investigator must assess the severity/intensity of the event.

Mild

- Asymptomatic or mild symptoms; clinical or diagnostic observations only
- Intervention not indicated
- Activities of Daily Life (ADLs) minimally or not affected
- No or minimal intervention/therapy may be required

Moderate

• Symptom(s) cause moderate discomfort

- Local or noninvasive intervention indicated
- More than minimal interference with ADLs but able to carry out daily social and functional activities.
- Drug therapy may be required

Severe (could be nonserious or serious)

- Symptoms causing severe discomfort/pain
- Symptoms requiring medical/surgical attention/intervention
- Interference with ADLs, including inability to perform daily social and functional activities (eg, absenteeism and/or bed rest)
- Drug therapy is required.

The term "severe" is often used to describe the intensity of a specific event (as in mild, moderate, or severe myocardial infarction); the event itself, however, may be of relatively minor medical significance (such as severe headache). This criterion is not the same as "serious," which is based on subject/event outcome or action criteria associated with events that pose a threat to a subject's life or functioning.

Seriousness, not severity, serves as a guide for defining regulatory obligations.

14.2.3 Causality

The Investigator must determine the relationship between the administration of IP and the occurrence of an AE/SAE as Not Suspected or Suspected as defined below:

Not Suspected: Means a causal relationship of the AE to IP administration is **unlikely or**

remote, or other medications, therapeutic interventions, or underlying conditions provide a sufficient explanation for the observed event.

Suspected: Means there is a **reasonable possibility** that the administration of IP

caused the AE. 'Reasonable possibility' means there is evidence to

suggest a causal relationship between the IP and the AE.

Causality should be assessed and provided for every AE/SAE based on currently available information. Causality is to be reassessed and provided as additional information becomes available.

If an event is assessed as suspected of being related to a comparator, ancillary, or additional IP that has not been manufactured or provided by PPM SERVICES SA, the name of the manufacturer when reporting the event will be provided.

14.2.4 Duration

For both AEs and SAEs, the Investigator will provide a record of the start and stop dates of the event.

14.2.5 Action Taken

The Investigator will report the action taken with IP as a result of an AE or SAE, as applicable (eg, discontinuation, interruption, or reduction of IP, as appropriate), and report if concomitant and/or additional treatments were given for the event.

14.2.6 Outcome

The Investigator will report the outcome of the event for both AEs and SAEs. All SAEs that have not resolved upon discontinuation of the subject's participation in the study must be followed until recovered, recovered with sequelae, not recovered, or death (due to the SAE).

14.3 Abnormal Laboratory Values

An abnormal laboratory value is considered to be an AE if the abnormality:

- results in discontinuation from the study;
- requires treatment, modification/interruption of IP dose, or any other therapeutic intervention; or
- is judged to be of significant clinical importance.

Regardless of severity grade, only laboratory abnormalities that fulfill a seriousness criterion need to be documented as an SAE.

If a laboratory abnormality is one component of a diagnosis or syndrome, then only the diagnosis or syndrome should be recorded on the AE page/screen of the eCRF. If the abnormality was not a part of a diagnosis or syndrome, then the laboratory abnormality should be recorded as the AE. If possible, the laboratory abnormality should be recorded as a medical term and not simply as an abnormal laboratory result (eg, record thrombocytopenia rather than decreased platelets).

14.4 Pregnancy

All pregnancies or suspected pregnancies occurring in either a female subject or partner of a male subject are immediately reportable events.

14.4.1 Females of Childbearing Potential

Pregnancies and suspected pregnancies (including a positive pregnancy test regardless of age or disease state) of a female subject occurring while the subject is on IP, or within 28 days of the subject's last dose of IP, are considered immediately reportable events. Investigational product is to be discontinued immediately. The pregnancy, suspected pregnancy, or positive pregnancy test must be reported to PPM SERVICES SA Drug Safety immediately by facsimile, or other appropriate method, using the Pregnancy Initial Report Form, or approved equivalent form.

The female subject may be referred to an obstetrician-gynecologist or another appropriate healthcare professional for further evaluation.

The Investigator will follow the female subject until completion of the pregnancy and must notify PPM SERVICES SA Drug Safety immediately about the outcome of the pregnancy (either normal or abnormal outcome) using the Pregnancy Follow-up Report Form, or approved equivalent form.

If the outcome of the pregnancy was abnormal (eg, spontaneous abortion), the Investigator should report the abnormal outcome as an AE. If the abnormal outcome meets any of the serious criteria, it must be reported as an SAE to PPM SERVICES SA Drug Safety by facsimile, or other appropriate method, within 24 hours of the Investigator's knowledge of the event using the SAE Report Form, or approved equivalent form.

All neonatal deaths that occur within 28 days of birth should be reported, without regard to causality, as SAEs. In addition, any infant death after 28 days that the Investigator suspects is related to the in utero exposure to the IP should also be reported to PPM SERVICES SA Drug Safety by facsimile, or other appropriate method, within 24 hours of the Investigator's knowledge of the event using the SAE Report Form, or approved equivalent form.

